Specific Aim 1: Test the hypothesis that clopidogrel monotherapy is safe following successful PCI among 100 consecutive patients with HBR and meeting the inclusion criteria (100 *active* patients, excluding patients who have been enrolled then withdrawn for various reasons such as starting an additional blood thinner, patient preference, etc.). To ensure that we have data on 100 active patients that complete their 1 month visit, we will plan to accrue up to 150 patients. The primary safety end point will be showing noninferiority of clopidogrel monotherapy in reducing ischemic events stratified by presence or absence of *CYP2C19* LOF allele (QuantStudio with Chemagic DNA extraction). All patients will receive clopidogrel (600 mg load & 75 mg maintenance) and aspirin (324 mg load & 81 mg maintenance) for the first week. Those with *CYP2C19* 2* or 3* LOF allele (*CYP2C19* LOF carriers) will be prescribed prasugrel or ticagrelor [prasugrel 60 mg load, maintenance 10 mg or 5 mg (for patients \geq 75 years or $<$ 60 kg) daily or ticagrelor 180 mg load, maintenance 90 mg twice daily (dose escalation with bolus will occur regardless of the timing of the last clopidogrel dose)]. Non-carriers (or those with inconclusive results) will continue with clopidogrel 75 mg daily maintenance dose. Aspirin will be stopped in all patients once *CYP2C19* results are available.

Specific Aim 2: Among participants enrolled in aim 1, aim 2 will determine the incidence of BARC 3 or 5 bleeding events. Other secondary endpoints are post-dismissal all-cause death, any MI up to 180 days, repeat revascularization, or any other BARC bleeding episodes.

SIGNIFICANCE

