- Design Overview.** For *Aim 1*, up to 150 participants with HBR on DAPT with clopidogrel and aspirin, who have undergone successful PCI will be stratified by the *CYP2C19* LOF allele within one week of DAPT initiation. If present, participants will be given prasugrel or ticagrelor monotherapy, and non-carriers will continue with clopidogrel monotherapy. The primary safety endpoint will be a composite of post-dismissal cardiac death/spontaneous MI <30 days or stent thrombosis <90 days of discharge. For *Aim 2*, the same subjects will undergo post-dismissal assessment for BARC 3 or 5 bleeding, all-cause death, any MI, and/or repeat revascularization up to 180 days. Informed consent followed by genotype assessment will be obtained prior to discharge. Loading dose of clopidogrel (600 mg) will be given to all patients and maintenance dose of 75 mg daily will be given, as indicated. We will allow patients to be given loading dose (324 mg) of aspirin either before or at the time of PCI. The choice of stents, access site and treatment site will be at the discretion of the treating physician (**Figure 1**).
- Clopidogrel and prasugrel/ticagrelor administration.** This study will be single-center, single-arm, open label, first-in-human, and a proof-of-concept, pilot and safety study. All participants in the first week will receive clopidogrel bolus (600 mg) and maintenance (75 mg) and aspirin bolus (324 mg, if not on aspirin) and 81mg maintenance. Participants with HBR who meet the inclusion criteria will be stratified by *CYP2C19* LOF allele. Non-carriers (or those with inconclusive results) will continue with maintenance dose of clopidogrel monotherapy at 75 mg daily. If LOF allele is present, they will be prescribed either prasugrel or ticagrelor monotherapy [prasugrel 60 mg load, maintenance 10 mg daily; ticagrelor 180 mg load, maintenance 90 mg twice daily; dose escalation with bolus regardless of timing of the last clopidogrel dose]. Prasugrel will be the preferred agent except when absolutely contraindicated (history of stroke/transient ischemic attack or active bleeding). Patients ≥ 75 years or < 60 kg will receive prasugrel at a reduced dose of 5 mg daily. If there is

Figure 1: Study Flow Chart

a relative contraindication to prasugrel (as determined by the treating physician), the participant will be given ticagrelor. Maintenance aspirin will be discontinued in both arms once genotype testing has been confirmed. (**Figure 1**).

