 - c) **Subject Accrual Plan:** The recruitment will be drawn from the Earl Wood Cardiac Catheterization Laboratory (>1,500 PCIs/year) and Cardiology inpatient services at St. Mary's Hospital. Day 1 will include screening following successful PCI, bleeding risk calculation (ARC-HBR), enrollment, informed consent, and clinical CYP2C19 assay collection. On day 30, a study coordinator phone call will occur to assess ischemic symptoms, readmission, and bleeding. On day 90, a study coordinator phone call will again assess ischemic symptoms, readmissions, and bleeding. All encounters will include drug education and assurance of compliance.
 - d) **Reassessment:** The study coordinator will make phone calls at one and three months to inquire about ischemic symptoms, readmissions at other hospitals with MI, or any bleeding.
7. **Control Cohort:** A cohort of similar patients will be identified from the Mayo Clinic catheterization laboratory PCI registry to determine rates of ischemic and bleeding events in a cohort of HBR post-PCI patients receiving standard of care DAPT after PCI. These patients will be identified by registry review, and we will utilize ICD diagnosis codes to identify bleeding and ischemic events. Retrospective chart review will verify the clinical situation to ensure the validity of the coded diagnoses (to minimize errors inherent to diagnosis coding). There will be no direct patient contact, and patients who refused registry research participation will be excluded from this study. We aim to obtain the following

data:

A. Events

- Event type (category below); diagnosis codes selected from Mayo Clinic database of ICD codes (<https://intranet.mayo.edu/charlie/quantitative-health-sciences-groups/rochester-epidemiology-project/index-of-possible-codes-for-specific-conditions-diseases/>)
- Date of ischemic/bleeding event
- Bleeding Categories
 - *Hemorrhage, gastrointestinal*
 - *Stroke (hemorrhagic)*
 - *Disease, cerebrovascular (hemorrhagic)*
 - *Hematuria*
- Ischemic Categories
 - *Infarction, myocardial*
 - *Disease, cerebrovascular (TIA, ischemic stroke)*

B. Inclusion

- Successful PCI
- Approx. 1 year date range TBD (n = 1500 patients; targeting contemporary PCI patients within the last 2 years).

C. Exclusion

- Enrolled in CHAMP Trial

D. Demographic/Procedure Info to Capture from PCI Registry

- Age/DOB
- Sex
- Race
- Event type (STEMI, NSTEMI/unstable angina, chronic CAD)
- PCI date
- Hemoglobin at time of PCI

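### Specific Aim 1 makes noninferiority of clopidogrel monotherapy the primary safety end point, which conflicts with the single-arm design, the switch of LOF carriers off clopidogrel, and the event composite defined in the Design Overview

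*Combined protocol and SAP*

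**What the plan says.** Specific Aim 1 sets the primary claim: "The primary safety end point will be showing noninferiority of clopidogrel monotherapy in reducing ischemic events stratified by presence or absence" of the LOF allele. It frames the hypothesis on 100 active patients, with accrual of up to 150.

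Other sections describe something different:

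- **Design.** General Methods, item 2: "This study will be single-center, single-arm, open label, first-in-human, and a proof-of-concept, pilot and safety study".
- **Primary endpoint.** Design Overview: "The primary safety endpoint will be a composite of post-dismissal cardiac death/spontaneous MI <30 days or stent thrombosis <90 days of discharge". No reference group or threshold is attached.
- **Treatment by genotype.** Design Overview, on the LOF allele: "If present, participants will be given prasugrel or ticagrelor monotherapy, and non-carriers will continue with clopidogrel monotherapy". Patients with inconclusive results also stay on clopidogrel.
- **Target of the question.** The Aim 1 Detailed Approach and its Expected Outcomes ask about safety, or increased ischemic risk, in non-carriers. They do not mention noninferiority.
- **Registry cohort.** General Methods, item 7 gives its purpose as "to determine rates of ischemic and bleeding events in a cohort of HBR post-PCI patients receiving standard of care DAPT after PCI". The listed ischemic categories are myocardial infarction and "Disease, cerebrovascular (TIA, ischemic stroke)". Its inclusion entry reads "Approx. 1 year date range TBD (n = 1500 patients; targeting contemporary PCI patients within the last 2 years)", whereas the section on reducing ischemic hazard speaks of as many controls as participants.

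The only other use of the term noninferiority is in the introduction, about a previously published trial.

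**The concern.** A noninferiority claim needs a population on the test treatment, a reference, a margin and a decision rule. The sentence in Specific Aim 1 supplies none of these clearly, and part of it contradicts the treatment plan. Read literally, it asks for a result on clopidogrel monotherapy in patients who are taken off clopidogrel.

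What is at stake is the trial's main conclusion. If no rule is fixed in advance, the meaning of noninferior would be settled after the events are known. The same result, for example 3 events in 60 non-carriers, could be reported as noninferior or as inconclusive. Expected Outcomes under Aim 2 goes further: if the data agree, it anticipates having shown that clopidogrel monotherapy is both safe and effective. The setting is one where the plan itself says that shorter DAPT must be weighed against ischemic risk.

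**Working it through.** **1. The plan's own figure.** The target of 100 active patients cannot be reproduced. No rate, margin, alpha or power is given for it. The step from 100 to 150 corresponds to a loss of 50/150 = 33.3%, but no dropout rate is stated.

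**2. The passages side by side.**

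| Element of the claim | What the rest of the plan provides |
|---|---|
| Clopidogrel monotherapy, LOF present | Carriers receive prasugrel or ticagrelor, so there is no information |
| Clopidogrel monotherapy, LOF absent | Non-carriers: 50%-70% of 100 = 50-70 patients (60%-70% in the Aim 2 Background), plus any inconclusive results |
| Noninferior to what | Not stated; the registry cohort is a candidate but is not named as the reference |
| On what endpoint | Cardiac death, spontaneous MI and stent thrombosis in the trial; MI and TIA/ischemic stroke listed for the registry |
| Margin, alpha, test | None in the available text |

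**3. What the sample size can show.** Exact (Clopper-Pearson) two-sided 95% limits for x events in n patients are the 2.5% quantile of Beta(x, n−x+1) and the 97.5% quantile of Beta(x+1, n−x). With x = 0, the upper limit is 1 − 0.025^(1/n).

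| Events / n | Observed rate | Exact 95% CI |
|---|---|---|
| 3/50 | 6.0% | 1.3%-16.5% |
| 3/60 | 5.0% | 1.0%-13.9% |
| 3/70 | 4.3% | 0.9%-12.0% |
| 5/100 | 5.0% | 1.6%-11.3% |
| 0/50 | 0% | 0%-7.1% |
| 0/70 | 0% | 0%-5.1% |

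The event counts are illustrative. The first four rows lie near 5%, the 30-day rate of death or MI in Table 2 for 2016 and 2017. Table 2 is only a proxy: it counts all death or MI after PCI and is not labelled as high bleeding risk.

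**4. Power, under my own assumptions.** Suppose a fixed goal of 10% and a one-sided 2.5% exact test. Success means that the upper limit lies below 10%. Power = P(X ≤ c), where X is binomial and c is the largest passing count. For n = 100, c = 4 and the attained alpha is 2.4%.

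| True rate | Power, n = 100 |
|---|---|
| 5% | 44% |
| 3% | 82% |
| 2% | 95% |

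In the non-carrier range, power does not rise smoothly, because c is a whole number. At a true 5% it is 8% at n = 50 (c = 0), 24% at n = 54 (c = 1), 13% at n = 69 (c = 1) and 31% at n = 70 (c = 2). A single power figure for this subgroup would therefore mislead.

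**The case against.** **A rule may exist in text that is not available.** The text stops in the middle of a list under Aim 2, Potential Problems, just before the bibliography. References 28 to 34 are cited nowhere in what precedes. A statistical section may have been lost. This stands: a reader might infer that the sponsor planned noninferiority with no margin or test at all, and the documents do not support that. It does not remove the conflict within Specific Aim 1.

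**Single-arm does not rule out noninferiority, and a control cohort is planned.** Both are correct. A single arm can be tested against a fixed goal, and the registry cohort on standard DAPT is a possible reference, so it would be wrong to say that no comparator exists. But no section ties the cohort to the claim, its size is described in two ways, and its ischemic list does not match the composite. Chart review might recover deaths, since Table 2 shows that the institution reports them. Stent thrombosis is the harder gap.

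**Stratified may mean treatment assigned by genotype.** The Design Overview and Aim 1 use the word that way. On that reading, the sentence loosely names the whole strategy. This is a fair reading, but the sentence still names clopidogrel monotherapy as what is to be shown noninferior, and under the strategy some patients do not receive it.

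**The study is underpowered.** This stronger reading is tempting, but the documents do not support it. The goal and alpha are mine, Table 2 is a proxy, and the trial enrolls after event-free PCI and excludes high-risk lesions, so its true rate may be below 5%. At 2% to 3%, 100 patients have good power against 10%.

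**Conclusion.** The sentence in Specific Aim 1 is wrong as written and should be changed before results are analyzed, because it defines the primary conclusion. Confidence is high for the internal conflict: the clopidogrel claim spans a carrier stratum that does not receive the drug, the defined endpoint is an event composite without a comparison, and no section links the registry cohort to the claim. Confidence is lower that margin, alpha and test are truly absent, given the break in the text.

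As described, the design can estimate a rate. With about 50 to 70 non-carriers, even zero events leaves an upper limit of 7.1% to 5.1%, and 3 in 60 leaves 13.9%. Whether such a limit would be good enough depends on a margin that the available text does not give. The intervals rest only on the assumed counts and the plan's 50%-70% share of non-carriers. The power figures rest on further assumptions and are not part of the conclusion.

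**What to change.** Replace the primary end point sentence in Specific Aim 1 with: *The primary safety objective is to estimate the rate of the primary composite (Design Overview) with an exact two-sided 95% CI, (a) in all patients on the genotype-guided aspirin-free strategy and (b) in patients on clopidogrel monotherapy, with confirmed non-carriers and inconclusive genotypes also shown separately.*

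Then:

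- Base any statement about clopidogrel monotherapy on (b), and report carriers on prasugrel or ticagrelor descriptively.
- Bring the remaining language into line with estimation: the hypothesis-testing wording in Specific Aim 1 and in the Aim 1 Detailed Approach, the aim of determining increased ischemic risk in Aim 1 Expected Outcomes, and the safety-and-efficacy conclusion in Aim 2 Expected Outcomes.
- Label the registry comparison descriptive.

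If a noninferiority rule does exist in text not available here, keep the claim only for a named population. State the comparator, margin, alpha and test in Specific Aim 1, and measure the comparator on the same composite.

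The estimation route needs no extra patients and no change to treatment. It requires edits in several sections and a separate display of inconclusive genotypes. The cost is a more modest claim: a rate and its interval instead of noninferiority. How withdrawn patients enter the denominator and which years of Table 2 to cite are separate questions, and this change does not settle them.

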3. **Medication adherence, provision of prasugrel/ticagrelor and follow-up:** Each enrolled participant will be carefully followed, pre-dismissal education about medication compliance and potential switch to prasugrel or ticagrelor will be given to each participant. A phone call by the study coordinator informing the participant about the results of genotype will be made within the first week of PCI. Study coordinator will mail 3-month supply of prasugrel or ticagrelor to patients with CYP2C19 LOF allele and contact them for the receipt of the medication and will instruct initiation of the loading and maintenance dose. The number of remaining tablets (pill count) at 3-month follow-up will be counted and recorded to assess adherence using a drug accountability report at 3 months. Non-carriers will continue clopidogrel monotherapy. Our main aim is to ensure safety of the participants. Close monitoring and follow-up of each patient will be done. Study-related events will be assessed by the study coordinator at hospital discharge and at 1 and 3 months after PCI by telephone. If patients could not be reached by telephone after multiple attempts, the site coordinator will conduct a medical record review to assess follow-up. All cardiovascular-related end points and hospitalizations will be reviewed and adjudicated by an independent committee blinded to study groups and P2Y12 inhibitor received by the patient. Only study-related events confirmed by the adjudication committee will be included in the analysis.
4. **Trial Duration:** 90 days. This is based on the observations that the highest bleeding and ischemic risk following PCI is within first 90 days. Importantly, a post-hoc analysis demonstrated an almost 80% risk reduction for ischemic events with genotype guidance in the first 3 months after PCI.

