2. **Assessment of CYP2C19LOF Allele:** Clinical CYP2C19 assay will be run on QuantStudio with Chemagic DNA extraction that assesses CYP2C19 (*2, *10, *17, *35) The results will be expected within 72 hours of receipt of the samples. Once received, the results will be communicated to the participants and clopidogrel monotherapy will be initiated or samples of prasugrel or ticagrelor will be mailed.

Expected Outcomes. From these data, we will determine whether there is increased ischemic risk in HBR non-carriers of CYP2C19 LOF genotype receiving clopidogrel monotherapy post-PCI. Close monitoring of participants receiving clopidogrel monotherapy or prasugrel/ticagrelor monotherapy for any cardiac deaths, spontaneous MI and stent thrombosis will be done.

Potential Problems and Alternative Strategies. The results of genotype-based assay will be available at or following the participant's discharge. To ensure compliance with clopidogrel monotherapy or switch among participants with CYP2C19 LOF allele, the study coordinator will call them with the results, mail the 90-day prescription for prasugrel or ticagrelor and ensure its receipt and initiation. Based on the expert consensus, pharmacodynamic data, escalation in patients with *CYP2C19 2* or 3*LOF allele* will require stopping clopidogrel and switching to 60 mg loading dose of prasugrel or 180 mg loading dose of ticagrelor regardless of the timing of the last dose of clopidogrel followed by standard maintenance dose of prasugrel 10 mg daily (5 mg if age ≥ 75 years or weight < 60 kg) or ticagrelor 90 mg twice daily. We have elected to exclude patients on chronic warfarin or DOAC. While this is an ARC major criterion for HBR, aspirin is already being discontinued frequently post-PCI in many patients to avoid triple therapy, and we want to ensure that this study is truly evaluating antiplatelet monotherapy and is not confounded by use of chronic anticoagulants. Patient enrollment is another potential problem, but our group has a strong track record of successfully enrolling participants into

Table 1: Criteria for High Bleeding Risk at the Time of Percutaneous Coronary Intervention

| Major | Minor |
|---|---|
| | Age ≥ 75 years |
| Anticipated use of long-term oral anticoagulation | |
| Severe or end-stage chronic kidney disease (eGFR <30 mL/min) | Moderate chronic kidney disease (eGFR 30 to 59 mL/min) |
| Hemoglobin <11 g/dL | Hemoglobin 11.0 to 12.9 g/dL for men and 11.0 to 11.9 g/dL for women |

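### Aspirin stops in every patient at the CYP2C19 result, but carriers' prasugrel or ticagrelor is mailed after it, and no visible text bridges the interval

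*Combined protocol and SAP*

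**What the plan says.** Two triggers govern the switch.

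**Stopping aspirin.** Specific Aim 1: "Aspirin will be stopped in all patients once" the CYP2C19 result is available. General Methods item 2: "Maintenance aspirin will be discontinued in both arms once genotype testing has been confirmed". Neither sentence exempts carriers or mentions the replacement drug.

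**Starting the carriers' drug.** Under Aim 1, Research Design item 2, "The results will be expected within 72 hours of receipt of the samples", and once they are in, "samples of prasugrel or ticagrelor will be mailed". General Methods item 3 has the coordinator mail a 3-month supply, then "contact them for the receipt of the medication and will instruct initiation of the loading and maintenance dose". The telephone call giving the genotype "will be made within the first week of PCI". Aim 1, Potential Problems and Alternative Strategies, adds "The results of genotype-based assay will be available at or following" discharge, and has the coordinator "mail the 90-day prescription for prasugrel or ticagrelor and ensure its receipt and initiation".

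**Text pointing to a simultaneous switch.** Specific Aim 1 and General Methods item 2 put everyone on clopidogrel plus aspirin in the first week. Aim 1: Detailed Approach has carriers receive prasugrel or ticagrelor within the first week of DAPT. The Schedule of Events puts the aspirin stop and the drug change in a single row.

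**The concern.** The aspirin stop is tied to the result. The new drug is tied to a later event, the arrival of a parcel and a further contact. Between the two, a carrier whose drug is mailed takes clopidogrel alone. Aim 1: Detailed Approach rests on the premise that carriers cannot convert clopidogrel effectively to its active form, and it reserves clopidogrel monotherapy for non-carriers.

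The interval falls early after PCI. Proposed Strategy to Reduce Ischemic Hazard describes MI as the dominant cause of cardiac death in the first week and mortality risk as raised for two weeks. The study also takes ACS patients. An event after dismissal in this interval would count in the primary safety endpoint (cardiac death or spontaneous MI before 30 days, stent thrombosis before 90 days), although it arose on a regimen not meant for carriers. The adherence measure described, a pill count at 3 months, would not by itself date the switch.

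**Working it through.** The plan gives no figure for this interval, so there is none to reproduce. The check sets the rules in order and then sizes the group and the interval.

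**Sequence for a carrier at home, read literally**

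1. The result arrives, at or after discharge (Aim 1, Potential Problems and Alternative Strategies).
2. Aspirin stops (Specific Aim 1; General Methods item 2).
3. The drug is mailed (Research Design item 2; General Methods item 3).
4. The coordinator contacts the patient about receipt and instructs the load (General Methods item 3).
5. Clopidogrel stops at the switch (Potential Problems and Alternative Strategies), so it implicitly continues from step 2 to step 4.

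From step 2 to step 4 the patient takes clopidogrel alone. The check on receipt and initiation controls when the interval ends. It does not say what the patient takes during it.

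**Number of carriers** (100% minus the non-carrier share)

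| Source of non-carrier share | Carriers | Per 100 active | Of 150 accrued |
|---|---|---|---|
| Opening background and Aim 1: Detailed Approach, 50-70% | 100 − 70 = 30% to 100 − 50 = 50% | 30-50 | 150 × 0.30 = 45 to 150 × 0.50 = 75 |
| Aim 2 Background, 60-70% | 100 − 70 = 30% to 100 − 60 = 40% | 30-40 | 150 × 0.30 = 45 to 150 × 0.40 = 60 |

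These counts are all carriers, the most who could be affected. Anyone handed the drug directly has no interval.

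**Length of the interval**

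- Result day: blood draw on Day 1, receipt by the laboratory the same day (assumption), plus 72 hours = 1 + 3 = Day 4.
- If the first-week target is met, the new drug starts by Day 7. Under the stop-at-result rule the interval is at most 7 − 4 = 3 days, so 0-3 days.
- An earlier result lengthens it. The extracted schedule appears to open the result call at Day 2, which would allow up to 7 − 2 = 5 days.
- A result call on Day 7, which General Methods item 3 allows, leaves 7 − 7 = 0 days for mailing. The target is then missed if the drug is mailed, and the text sets no upper limit on the interval.
- Aspirin kept through Day 7 with the target met: 0 days.
- Mailing time is not stated. If transit plus the receipt call took 1 to 5 days (assumption), the interval would be 1 to 5 days under the stop-at-result rule and 0 days if aspirin stopped at the load.

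**The case against.** The best counter-argument is that the intended design is clear and protects carriers. Aim 1: Detailed Approach limits clopidogrel monotherapy to non-carriers. Research Design item 2 presents two alternatives at the result: non-carriers begin monotherapy, carriers are sent drug. On that reading monotherapy does not begin for carriers at the result. Two sections keep everyone on aspirin in the first week. The schedule separates the result call from the row that joins the aspirin stop to the drug change. The availability of the result could also be read as the earliest time to stop aspirin, not the day to stop it. Figure 1 is cited directly after the aspirin sentence in General Methods item 2 and was not available.

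This shows what was probably meant. It does not make the aspirin stop conditional on the new drug anywhere, and the two sentences that govern aspirin cover carriers expressly. The intent therefore conflicts with the stated dosing rule and leaves it in place.

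Several limits do stand:

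- No patient is untreated, since clopidogrel continues.
- The length of the interval is not established.
- Stent thrombosis risk is described as low, and several high-risk lesion types are excluded.
- Whether dose dates are captured depends on a case report form not in these documents. The drug accountability report and the Day 7 ± 2 call may help.
- Extending aspirin without a limit would be a weakness in high-bleeding-risk patients, so the fix should set one.

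**Conclusion.** The concern holds. The protocol's aspirin rule, followed as written, leaves carriers supplied by mail on clopidogrel alone from the result until the new loading dose, and no visible text prevents this. Up to 30-50 of 100 active participants (45-75 of 150 accrued) could be affected. The interval is 0-3 days under a Day 4 result and a first-week switch; it is zero if the drug is handed over and has no stated upper bound if mailing runs past the first week. These lengths assume same-day sample receipt, and the mailing time is unknown. The absolute risk is probably small. The point should still be fixed: it concerns patient safety and treatment fidelity within the primary endpoint window, and two reasonable readings lead to different treatment. Confidence is medium, mainly because Figure 1 was not available.

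**What to change.** In Specific Aim 1, General Methods item 2 and Aim 1: Detailed Approach, state that:

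- non-carriers and patients with inconclusive results stop aspirin at the result;
- carriers continue aspirin 81 mg and clopidogrel until the prasugrel or ticagrelor loading dose is confirmed taken, or the drug is dispensed locally at the result;
- a maximum interval from result to load applies, with local dispensing if the mailed supply will not meet it.

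Align the first-week wording in Specific Aim 1 and General Methods item 2 with this rule, and check Figure 1 against it. Record the dates of the last aspirin dose and the first prasugrel or ticagrelor dose, if the case report form does not already, so that events in between can be identified.

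The cost is one sequencing statement in three places and at most two date fields. The clinical cost is some extra days of aspirin with clopidogrel in carriers at high bleeding risk. With the interval capped, that stays well below the DAPT duration of at least 30 days that the Significance section gives as standard of care.
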